5. I agree to maintain adequate and accurate records in accordance with CHR policies, Federal, state and local laws and regulations.

UCSF Principal Investigator/Study Chair

Printed Name

Signature

Date

Participating Sites

Robert H. Lurie Comprehensive Cancer Center
Northwestern University

Principal Investigator

Site

Printed Name

Signature

Date

Abstract

Title	Phase II Trial of the Combination of Temozolomide and Sorafenib in Advanced Hepatocellular Carcinoma
Patient population	Histologically-confirmed, advanced, treatment-naïve HCC with Child-Pugh A or B7 liver dysfunction
Rationale for Study	To determine efficacy of and explore biomarkers for response to combination of temsirolimus plus sorafenib in advanced HCC
Primary Objective	To determine the median time to progression (TTP) in patients with advanced HCC treated with combination of temsirolimus plus sorafenib
Secondary Objectives	
 1. To determine response rate (RR) using RECIST 1.1 2. To measure median progression-free survival (PFS) 3. To measure median overall survival (OS) 4. To measure time to treatment failure (TTF) 5. To measure change in AFP tumor marker and examine for association between change in AFP and TTP and best response 6. To characterize toxicity and tolerability of the combination of temsirolimus plus sorafenib 7. To describe TTP, PFS, OS, response rate, AFP response, and toxicity and tolerability in subsets defined by HBV, HCV, Asian, and non-Asian status
Study Design	Single-arm, one-stage, open-label phase II trial to evaluate the efficacy of the combination of temsirolimus plus sorafenib in first line therapy for patients with histologically-confirmed advanced HCC.
Number of patients	Target sample size is 25 patients, expected maximum enrollment is 28 patients.
Duration of Therapy	Individual patient treatment will continue indefinitely from the time of enrollment, until unacceptable toxicity, unmanageable toxicity despite optimal supportive care and dose modifications, clinical disease progression or progression per RECIST 1.1, withdrawal of consent by the patient, or the decision to discontinue treatment by the treating physician due to changes in the patient's condition or other factors which may influence safety or compliance.
Duration of Follow up	After treatment discontinuation, follow up for overall survival monitoring will be performed for up to 5 years or until death, whichever comes first.
Duration of study	The study will reach completion approximately 24 months from the time the study opens to accrual. The study will end 5 years after the final patient discontinues treatment or after all patients are deceased, whichever comes first.

Abstract

Study Drugs
	
Temsirolimus: 10 mg weekly will be administered intravenously over 30 to 60 minutes using an infusion pump starting on Cycle 1, Day 1 of study enrollment.
 
Sorafenib: 200 mg tablet twice daily starting on Cycle 1, Day 1 of study enrollment after completion of temsirolimus infusion.

Safety Assessments
	
Analyses will be performed for all patients having received at least one dose of study drug. The study will use the NCI (CTCAE) Version 4.0.

Efficacy Assessments
	
Primary Endpoint Median TTP will be calculated in months from date of first dose of protocol therapy to date of removal from study for progression; Kaplan-Meier methods will be used to summarize the primary endpoint (median TTP).
 
Secondary Endpoints Response rate (RR) will be measured by RECIST version 1.1; measurements will be presented descriptively for the study cohort.
 
Median PFS will be calculated in months from date of first dose of protocol therapy to date of documented disease progression or death from any cause. Kaplan-Meier methods will be used to summarize time-to-event outcomes including the primary endpoint (median TTP) and secondary endpoints (PFS, TTF, OS).
 
Median OS for all enrolled patients who receive at least one dose of protocol therapy will be calculated from date of first dose of protocol therapy until date of death, using chart review and/or follow up phone calls to determine date of death in patients after removal from study.
 
TTF will be measured from date of first dose of protocol therapy to date of study discontinuation for progression, death, or toxicity.
 
In patients with baseline AFP ≥ 20 ng/mL, AFP response will be measured by the percent change from baseline value to the value at the time of best AFP response. The change in AFP will also be examined for association with absolute TTP and best response.

Abstract


Efficacy Assessments (continued)
	
Exploratory Endpoints CTC will be enumerated in peripheral blood at baseline and after 1 and 2 cycles of therapy to evaluate for any relationship between baseline levels and change in levels with median TTP and/or OS; baseline level of CTC will be compared to proportion with TTP at 6 months to determine if there is an association using Fisher’s Exact tests. Change in CTC levels (increase or decrease) after 1 and 2 cycles will be compared to TTP to determine if there is an association using Fisher’s Exact tests. In all patients with active or chronic HBV infection, changes in HBV DNA quantitative by PCR will be characterized using descriptive statistics to calculate the proportion of patients with an increase or reactivation in viral load while on protocol therapy.

Unique Aspects of this Study
	
This Phase II trial is being developed following completion of a Phase I study of the combination of temsirolimus and sorafenib in 25 first-line therapy patients with advanced hepatocellular carcinoma (December 2009 through April 2012). The MTD and recommended phase II dose (RP2D) of the combination was temsirolimus 10 mg IV weekly plus sorafenib 200 mg PO BID.

List of Abbreviations

AE	adverse event
ALP	alkaline phosphatase
ALT	alanine aminotransferase
ANC	absolute neutrophil count
AST	aspartate aminotransferase
ATC	Anatomical Therapeutic Chemical (Classification System)
AUC	area under the curve
BUN	blood urea nitrogen
CBC	complete blood cell (count)
CHR	Committee on Human Research (UCSF IRB)
CR	complete response
CRC	Clinical Research Coordinator
CRF	case report form
CSF	cerebral spinal fluid
CT	computerized tomography
CTCEA	Common Terminology Criteria for Adverse Events
CTEP	Cancer Therapy Evaluation Program
CTMS	Clinical Trial Management System
DFS	disease-free survival
DLT	dose limiting toxicity
DSMC	Data and Safety Monitoring Committee
DSMP	Data and Safety Monitoring Plan
ECOG	Eastern Cooperative Oncology Group
FCBP	female of childbearing potential
FDA	Food and Drug Administration
GCP	Good Clinical Practice
HBeAg	Hepatitis B “e” antigen
HBV	Hepatitis B virus
HCC	Hepatocellular carcinoma
HCT	Hematocrit
HCV	Hepatitis C virus
HDFCCC	Helen Diller Family Comprehensive Cancer Center
HGB	Hemoglobin
HIV	human immunodeficiency virus
ICH	International Conference on Harmonization

List of Abbreviations

IND	investigational new drug application
IP	investigational product
IRB	Institutional Review Board

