3.2 Number of Subjects

The target sample size is 25 evaluable patients for the primary endpoint. With the expectation of approximately 10% ineligibility rate, the expected maximum enrollment will be 28 patients. Eligible patients who receive at least one dose of protocol therapy will not be replaced. Patients will be replaced and removed from study if determined to be ineligible after enrollment (for reasons such as inability to comply/withdrawal of consent or other ineligibility)

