- Initial assessment of response or progression will be made based upon standard of care Radiology review plus clinical assessment if RECIST 1.1 measurements are not available at the time of study visit. In patients without signs of clinical progression, progression must be confirmed by RECIST 1.1 prior to removal from study. If progression is identified by RECIST 1.1 that was not identified by standard of care Radiology review plus clinical assessment, a patient will be removed from study at date of next scheduled study visit. Efforts will be made to obtain RECIST 1.1 measurements for patients treated at both sites within approximately 7 days of start of odd cycles.
- Serum AFP tumor marker
- Blood specimen collection for CTC testing (Cycles 2 and 3 only)
- Banking of blood specimens (Cycles 3 and End-of-Treatment only)

6.1.3 6.1.2.3 Study Procedures Day 8, 15, and 22 of All Cycles after Cycle 1 (within 7 days)

- Weight measurement and vital signs including temperature, blood pressure, heart rate, pain score, and oxygen saturation
- Safety laboratory assessments: CBC w/Diff, complete metabolic panel (electrolytes, BUN, creatinine, glucose, calcium, magnesium, phosphorus, total bilirubin, direct bilirubin, alkaline phosphatase, albumin, AST, and ALT), INR

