9.1.4 Exploratory Endpoints

1. TTP, RR, PFS, OS, TTF, AFP response, and toxicity and tolerability will be described in subsets defined by HBV, HCV, Asian, and non-Asian status.
2. CTC will be enumerated in peripheral blood at baseline and after 1 and 2 cycles of therapy to evaluate for any relationship between baseline levels and change in levels with median TTP and/or OS.
3. Archival tumor specimens will be sectioned for IHC testing of selected mTOR pathway markers and next-generation sequencing. Markers will be dichotomized as high or low using published cutpoints to describe incidence of activation in study population and explore for relationship to clinical outcomes including TTP and AFP response.
4. In patients with chronic active HBV and/or positive HBcAb, hepatitis B viral DNA quantitative will be monitored for rates of viremia/reactivation on study.
5. Optional patient blood specimens (including serum, PBMC, whole blood, and plasma) and left-over archival pathology specimens will be banked in the UCSF Hepatobiliary Tissue Bank (HBTB) for future research.

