9.4.4 Exploratory Analyses/Assessments

- CTC levels: Baseline level of CTC (detectable or undetectable) will be compared to proportion with TTP at 6 months to determine if there is an association using Fisher's Exact tests. Change in CTC levels (increase or decrease) after 1 and 2 cycles will be compared to proportion with TTP at 6 months to determine if there is an association using Fisher's Exact tests. Markers of mTOR pathway activation: Descriptive statistics will summarize the IHC parameters of staining intensity, percentage positivity, distribution, and intracellular localization for each protein. Due to possible limited specimen quantity, IHC outcomes will be dichotomized. Activation will be measured by % positive cells and intensity using published IHC cutpoints for high/low: cytoplasmic pAkt > 40% or 2-3+, cytoplasmic PTEN intensity < 10% or 0-1+, cytoplasmic pS6RP > 70% or 2-3+, or LKB1 0-1.⁷⁻¹² Univariate analysis using Cox's model will be performed to test whether the dichotomized expression of each protein using the published cutpoints is a significant predictor of TTP. Results for each test will include the hazard ratio (HR) with 95% confidence intervals. The association between each protein and the two binary coding schemes for AFP decline ($\geq 50\%$ or $\geq 20\%$) on C2D1 will be tested using Fisher's exact test. Results for each test will be summarized with proportions with pathway activation and 95% confidence intervals for each AFP subset. Each patient will also be categorized as having overall mTOR pathway activation (defined as any combination of high pAKT, high pS6RP, low PTEN, and/or low LKB1) or not. This binary variable will also be examined for its relationship with TTP, OS, AFP response, and other clinical endpoints using the same methods described above. For each test of association with AFP change, based upon Fisher's exact test large differences can be detected (e.g. 10% among 7 patients with marker-low, 80% among 8 patients with marker-low) (power=81%, $\alpha_2=10\%$). The sample size is too small to test for a difference in TTP, OS, or other clinical endpoints according to pathway activation status. The expected sample size will be ≥ 25 cases (expect 40 to 45 cases) with IHC-quality archival tumor, with the expectation that $\sim 75\%$ of cases will be evaluable for TTP ($n \geq 18$) and 60% evaluable for AFP response on C2D1 ($n \geq 15$).

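### CTC is to be related to TTP and/or OS, but only Fisher's exact tests on 6-month TTP are specified: OS by CTC has no method, and time-to-event information on TTP goes unused

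*Combined protocol and SAP*

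**What the plan says.** Sections 2.3, 2.4.3 and 9.1.4 and the Abstract all state that CTC is counted at baseline and after 1 and 2 cycles "to evaluate for any relationship between baseline levels and change in levels with median TTP and/or OS".

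The methods appear in two places:

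- **Section 9.4.4, baseline:** "Baseline level of CTC (detectable or undetectable) will be compared to proportion with TTP at 6 months", by Fisher's exact test.
- **Section 9.4.4, change:** "Change in CTC levels (increase or decrease) after 1 and 2 cycles will be compared to proportion with TTP at 6 months", again by Fisher's exact test.
- **Abstract, baseline:** the same 6-month comparison: "baseline level of CTC will be compared to proportion with TTP at 6 months to determine if there is an association using" Fisher's exact test.
- **Abstract, change:** "Change in CTC levels (increase or decrease) after 1 and 2 cycles will be compared to TTP to determine if there is an association". Fisher's test is named, but no 6-month cut is given.

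Other markers are handled differently. Section 9.4.3 gives AFP Kaplan-Meier and log-rank analyses of TTP. In Section 9.4.4, univariate Cox models for the mTOR proteins "will be performed to test whether the dichotomized expression of each protein using the published cutpoints is a significant predictor of TTP", reported as hazard ratios with 95% confidence intervals. Overall pathway activation is also examined against OS.

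On sampling, Section 6.1.2.2 lists "Blood specimen collection for CTC testing (Cycles 2 and 3 only") on Day 1 of the cycle. The first restaging scan is also due at Cycle 3 Day 1.

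**The concern.** A 2x2 table at 6 months treats progression at week 8 like progression at week 24, and progression at 8 months like progression at 20 months. TTP is censored for toxicity, withdrawal or death without progression (Sections 2.4.1 and 9.1.2). A patient censored before 6 months is neither a success nor a failure, and the plan does not say where that patient goes. The Abstract's version for change in CTC does not define a table at all.

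OS is named in the objective and followed for up to 5 years (Section 3.5), yet no CTC method uses it.

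There is also a timing problem with the second on-treatment sample. It is drawn at the visit of the first scan, so anyone found to have progressed there is already a 6-month failure when the predictor is measured. An association could then reflect progression already present rather than prediction.

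At stake is the usefulness of the CTC results for planning later work. The primary endpoint, sample size and safety rules are not affected.

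**Working it through.** **1. The plan's own figures.** None is given for CTC. The nearest is the primary design: "The target sample size is 25 evaluable patients for the primary endpoint" (Section 3.2), with 88% power at one-sided 10% for a 6-month rate of 25% against 50% (Section 9.2.1). Exact binomial: requiring at least 10 of 25 successes gives alpha 7.1% and power 88.5%, so it reproduces. As a check on the Fisher code, the 81% power in Section 9.4.4 (10% of 7 against 80% of 8, two-sided 10%) comes out at 81.4% with a doubled one-sided p-value and 83.6% with the usual two-sided one.

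**2. Inputs for the CTC comparison.**

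- From the documents: N = 25; exponential TTP and uniform accrual (9.2.1); accrual over about 24 months with at least 6 months' potential follow-up (3.7), modelled as follow-up uniform on 6-30 months; scans every 8 weeks (6.1.2.2).
- Assumed, because the documents give none: hazard ratio 2, 3 or 4 (medians 3 v 6, 3 v 9, 3 v 12 months), two-sided 5%, and the split. A 12:13 split is close to the 45% detectable reported in Section 1.4.2 for a different assay.

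The 6-month progression-free probability is 2^(-6/median): 25% for a median of 3 months, 50% for 6, 63% for 9 and 71% for 12.

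**3. Power at the 12:13 split** (simulated, 3,000 trials per setting). Relative loss = 1 - Fisher/log-rank.

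| HR | Fisher, 6-month TTP | Log-rank, full TTP | Relative loss |
|---|---|---|---|
| 2 | 20.3% | 34.8% | 1 - 20.3/34.8 = 42% |
| 3 | 44.8% | 66.6% | 1 - 44.8/66.6 = 33% |
| 4 | 60.6% | 84.5% | 1 - 60.6/84.5 = 28% |

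**4. Matching test sizes.** Under no effect, Fisher's test rejects about 4.1% of the time and the log-rank test about 5.7%. With the log-rank test held to Fisher's actual size, a separate simulation gives 22% v 29%, 44% v 60% and 61% v 79%. The losses are 1 - 22/29 = 24%, 1 - 44/60 = 27% and 1 - 61/79 = 23%.

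**5. Uneven split.** At 20:5, size-matched power (Fisher v log-rank) is 15% v 12%, 30% v 32% and 40% v 44%. The gain has largely gone.

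**6. Early censoring.** Assume 25% are censored by 6 months for reasons other than progression. About 5 of 25 patients then have unknown 6-month status. If they are left out of the table at 12:13, Fisher v log-rank is 12% v 26%, 28% v 54% and 40% v 71% at nominal 5%.

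**7. Week-8 overlap.** Week 8 is 56/30.4375 = 1.84 months. The share progressed by then is 1 - 2^(-1.84/6) = 19% for a median of 6 months and 1 - 2^(-1.84/3) = 35% for a median of 3 months. These are upper bounds on the share of sampled patients, since anyone removed for clinical progression before the visit gives no sample. Suppose CTC has no predictive value, but 80-90% of these patients show a rise against 50% of the others (rates with no source in the documents). Fisher's test then rejects about 11-16% of the time at nominal 10%, and about 6-10% at nominal 5%. At nominal 10%, restricting to patients progression-free at that scan brings it to about 5-6%.

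**The case against.** The objective says TTP and/or OS, so a TTP-only analysis meets its literal wording. Six months is the trial's design threshold, and 6-month proportions are reported throughout Sections 9.4.2 and 9.4.3. These are exploratory analyses that feed no decision. Section 9.4.4 itself calls the sample too small to test TTP or OS by mTOR pathway status, and more cases are expected there than the 25 or so available for CTC. Even the log-rank test has only about 35% power at a hazard ratio of 2. With the slide-based assay used here, all 5 phase I patients tested had detectable cells (Section 1.4.2). If nearly everyone is detectable, no choice of outcome test rescues the baseline comparison.

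Most of this stands and limits the point to a cheap improvement. It does not explain why CTC alone lacks a time-to-event analysis, and it does not say what happens to patients censored early. For hypothesis generation, a hazard ratio with its interval is more useful than a p-value from a 6-month table.

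A reader might infer that OS is never analysed. That is not so: Section 9.4.3 summarises OS by Kaplan-Meier for the whole cohort. Only OS by CTC lacks a method.

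**Conclusion.** The mismatch holds. The CTC objective names TTP and/or OS, the only specified tests are Fisher's exact tests on 6-month TTP (uncut TTP for change in the Abstract), OS by CTC has no method, and early-censored patients have no defined place.

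The power cost is illustrative. At assumed hazard ratios of 2-4 and a near-even split it is about 28-42% of log-rank power at nominal two-sided 5%, and about a quarter at matched size. At 20:5 the size-matched difference is small. A reader might take a fixed fraction, such as a third, as a property of this plan. The documents do not support that, because they state no CTC effect, alpha or split, and part of the nominal gap is Fisher's conservatism.

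The overlap of the Cycle 3 Day 1 sample with the first scan is real and justifies a landmark. The size of any false-positive inflation is not established, because it depends on assumed CTC-rise rates. It concerns the change analysis only, not baseline CTC.

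**What to change.** In the Abstract and Section 9.4.4, analyse CTC against TTP and against OS by Kaplan-Meier and log-rank, with Cox hazard ratios and 95% confidence intervals. This follows what is planned for AFP (TTP) and the mTOR markers. Keep the 6-month proportion as a descriptive line, and make the Abstract and Section 9.4.4 agree on change in CTC.

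For change in CTC, start the clock at the sample visit (Cycle 2 Day 1 or Cycle 3 Day 1). For TTP, include only patients progression-free through that visit, counting the Cycle 3 Day 1 scan. Judge this by the scan result rather than the date of removal from study, because Section 7.1.1.5 allows removal at a later visit.

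The cost is a few sentences and a few lines of code, with no new data. Cox regression assumes proportional hazards, the landmark drops early progressors from the change analysis, and the results should still be labelled exploratory and underpowered for modest effects.

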1.1 Background on Indication

Hepatocellular carcinoma (HCC) is the third leading cause of cancer death worldwide with an incidence of over 600,000 new cases and almost as many deaths annually. (Parkin, Bray et al. 2005) Advanced stages of disease at diagnosis often preclude curative treatments, and the overall prognosis of patients diagnosed with advanced HCC remains dismal with median survival of approximately 8 months.(Llovet, Burroughs et al. 2003; El-Serag 2007; Llovet, Ricci et al. 2008) Historically, systemic therapies for advanced HCC have not been associated with a survival benefit, largely due to compromised hepatic function from underlying liver disease as well as intrinsic tumor chemoresistance.(Chenivesse, Franco et al. 1993; Soini, Virkajarvi et al. 1996; Jiang, Lu et al. 1997; Yeo, Mok et al. 2005; Lopez, Villanueva et al. 2006) In 2008, publication of the Sorafenib Hepatocellular Carcinoma Assessment Randomized Protocol (SHARP) phase III trial demonstrated a significant improvement in overall survival (OS) in patients with advanced HCC treated with the biologic agent, sorafenib.(Llovet, Ricci et al. 2008) The SHARP trial will be discussed in detail below. Despite improvements in outcome with sorafenib, however, the median OS for patients with advanced HCC remains less than a year.(Llovet, Ricci et al. 2008) Multiple recent randomized phase 3 trials of other anti-angiogenic multikinase inhibitors in HCC, including a first-line trial of sunitinib versus sorafenib and a second-line trial of brivanib versus placebo, have failed to show benefit, underscoring the challenges of toxicity, comorbidity, and chemoresistance in this notoriously treatment-refractory disease.(Cheng 2011; Llovet 2012) New active drugs and combinations are urgently needed.

1.2 Background on the Compounds

1.2.1 Sorafenib

Sorafenib is a small molecule bi-aryl urea with multikinase inhibitor activity. A primary target is the serine-threonine kinase, Raf-1, as well as mutant RET, mutant FLT-3, and wild-type and mutant c-KIT.(Bayer 2011) Sorafenib also has antiangiogenic activity, inhibiting receptor tyrosine kinases including vascular endothelial growth factor (VEGF) receptors 2 and 3 and the platelet derived growth factor receptor- β (PDGFR β). (Wilhelm, Carter et al. 2004; Liu, Cao et al. 2006; Chang, Adnane et al. 2007) Preclinical studies in HCC show that Raf-1 kinase signaling along with prolific tumor angiogenesis are common features, providing a molecular rationale for the efficacy of this agent.(Huynh, Nguyen et al. 2003; Semela and Dufour 2004; Calvisi, Ladu et al. 2006; Liu, Cao et al. 2006; Villanueva, Newell et al. 2007) In preclinical models of HCC including athymic mouse xenografts, sorafenib treatment produces both anti-tumor and anti-angiogenic effects.(Bayer 2011)

The metabolism of sorafenib is predominantly hepatic via oxidation by CYP3A4 and glucuronidation by UGT1A9.(Bayer 2011) Sorafenib is a moderate to strong inhibitor of CYP2C8, 2B6, 2C9, 2C19, 2D6, and 3A4 as well as UGT1A1 and 1A9. In cultured hepatocytes, sorafenib does not induce CYP1A2 or 3A4. Excretion is predominantly through biliary/fecal route. Bioavailability is moderate to high in animal models. Terminal half-life from plasma is 4 hours in dogs, 9 hours in rats, and 6 hours in mice. There is high plasma protein binding of 99.5%. The sorafenib metabolites M2 and M5 also potently inhibit VEGFR2, PDGFR β , and

FLT-3, though in xenograft models, M2 has lower efficacy than the parent compound. In preclinical models, sorafenib can be safely combined with multiple conventional cytotoxic agents including gemcitabine and cisplatin.

In human studies, there was evidence of accumulation up to 7-fold upon multiple dosing without further increase after 7 days of multiple dosing. The mean terminal elimination half-life in humans is 25 to 48 hours. It should be administered fasting or with a low- or moderate-fat meal, as high-fat meals decrease bioavailability. In humans, 19% of dose is excreted in urine and 77% in feces. M2 is the principle plasma metabolite. There is high inter-patient PK variability not explained by gender, age, weight, or hepatic function. Prior phase I studies of sorafenib have shown significant interpatient pharmacokinetic (PK) variability without clear relationship to toxicity.(Strumberg, Richly et al. 2005; Strumberg, Clark et al. 2007) The exposure values and PK are similar in patients with Child-Pugh A and B hepatic dysfunction. In a phase I study studying sorafenib in patients with organ dysfunction, there was no clear effect of renal or hepatic dysfunction on sorafenib clearance by PK measures, though toxicity was increased.(Miller, Murry et al. 2009) No dose adjustment is required for patients with mild to severe renal impairment not requiring dialysis. The mean AUC of sorafenib was 30% lower in Asians than Caucasians but does not appear to correlate with toxicity or efficacy. There was minimal impact on cardiovascular parameters in humans though there is a small to minimal mean prolongation of QT/QTc interval. Human metabolism is predominantly hepatic through CYP3A4-mediated oxidation and UGT1A9-mediated glucuronidation. It may be co-administered with CYP3A4 substrates and inhibitors without expected increase in exposure, though inducers such as rifampin may reduce sorafenib AUC. Alteration of GI flora by antibiotics may also reduce exposure. Other agents and classes with potential for drug interactions with sorafenib are reviewed in *Section 6.7 and Appendices 6-9 Prohibited Medications*.

Additional information on sorafenib is provided in *Section 4 Study Drugs* as well as in the Investigator's Brochure. (Bayer 2011)

